#### ***Rationale for biomarkers***

NFL is a biomarker correlated with prognosis and remain relatively stable over time. A change in the expression of NFL may, therefore, be considered as a potential disease amelioration in ALS (Verber et al., 2019). Plasma creatinine is a surrogate ALS biomarker of muscle mass and is decreased in ALS patients. Serum creatine kinase (CK) is increased in ALS patients and correlates with survival in some studies. Both are considered muscle denervation biomarkers in ALS. Urinary P75ECD is a surrogate ALS biomarker and is elevated in ALS patients. The three biomarkers are associated with disease progression (Verber et al., 2019). To measure the pharmacological effect (target engagement) of edaravone, oxidative stress biomarkers, like 8-OHdG, will be measured (Verber et al., 2019).

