**3.2.4. Exploratory Endpoints**

Pharmacokinetics

PK interaction between FAB122 and riluzole

Biomarkers

1. Change from baseline in the prognostic ALS biomarker neurofilament light (NFL)
2. Change from baseline in the ALS biomarkers creatinine and creatinine kinase
3. Change from baseline in the ALS biomarker Urinary extracellular domain of neurotrophin receptor p75 (Urinary P75ECD)
4. Change from baseline of oxidative stress biomarker 8-hydroxyguanosine (8-OHdG)

Health economics

Cost-Utility analysis of treatment with FAB122

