13. Optional CSF sampling will be performed (if consented) in about 30 patients at baseline, week 12, and week 24. Lumbar Puncture for CSF sampling is an aseptic procedure which needs standard bedside aseptic procedures with no-touch technique, sterile drapes and use of chlorhexidine or an equivalent antiseptic. Local anaesthesia with small amount of lidocaine can be infiltrated. A right-handed practitioner should position the patient in the left lateral decubitus position, with the vertebrae in line with the horizontal plane and the head in a neutral position and the knees flexed, also setting position could be applied if seemed by the practitioner. The bony landmark is the L4 spinous process and the L3/L4 interspace is recommended. Atraumatic 22-gauge needle could be used, however smallest diameter needle with which the practitioner can confidently perform the procedure avoiding an increased number of attempts should be chosen. 10 ml CSF sample will be drawn at each time point. After the procedure, a small sterile dressing is placed on the site and the patient can mobilise as soon as it is comfortable to do so. Regular analgesics such as paracetamol could be prescribed.

14. Only labs parameters that are abnormal in the screening visit will be re-evaluated in baseline visit.

\* In case it's necessary, NCS assessment can be performed during the baseline visit, provided the approval from the central reader are available prior to randomization.

In case that, due to ALS progression, the subject is not able to attend the clinic or perform specific testing such as HHD or SVC, at least ALSFRS score, adverse events and concomitant medication use will be collected (if necessary by telephone). For safety assessments, the on-site visits are key for the study. In case a subject is not able to attend the site for two consecutive visits IMP must be discontinued at the second missed visit. The patient can continue its participation in the trial, via telephonic visits to collect ALSFRS-R, Adverse Events and Concomitant Medication, as long as the subject does not withdraw consent.

The following sections provide details regarding the procedures to be performed at each study visit:

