**\* Only labs parameters that are abnormal in the screening visit will be re-evaluated in baseline visit.**

- Urine samples for urinalysis
- Urine pregnancy test only in women of childbearing potential
- Plasma vitamin B6 levels, and, if necessary, vitamin B6 supplements (pyridoxine (100 mg/day)) will be prescribed.
- ALS evaluation procedures: ALSFRS-R, Slow Vital Capacity (SVC), Hand-Held Dynamometry, ALSAQ-40, Edinburgh Cognitive and Behavioural ALS Screen (ECAS), EQ-5D-5L, VAS, King's staging system and MiToS.
- Blood sampling for biomarker: neurofilament light (NFL). Creatinine and creatine kinase will be measured in routine biochemistry lab testing.
- Urine collection for biomarkers: urinary extracellular domain of neurotrophin receptor p75 (Urinary P75ECD) and oxidative stress biomarker 8-hydroxyguanosine (8-OHdG)
- Blood sampling for genotyping for Future Biomedical Research (FBR) (if consented)

- Blood sampling for RNA and serum collection for FBR (if consented)
- Cerebrospinal fluid (CSF) sampling for Future Biomedical Research (if consented)
- Dispensing study Medication: Instructions for dosing FAB122 and first dosing
- Blood sampling for FAB122, in selected sites if consented. Specific ICF will be provided.
- Blood sampling for riluzole, in selected sites if consented. Specific ICF will be provided.
- Adverse Events monitoring
- Cost questionnaire

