# **5 STATISTICAL ANALYSIS**

## **5.1 General considerations**

Raw data (in listings) will be presented in the same precision as received. Appropriate rounding will be performed for the summary statistics: arithmetic mean, median, SD (standard deviation) and confidence limits will be presented with one more decimal than the original data; minimum and maximum values will be presented with the same precision as the original data. In frequency tables, percentages will be presented with 1 decimal. P-values will be presented with 3 decimals, and those smaller than 0.001 will be replaced by <0.001.

Descriptive statistics presented in general summary tables will be the number of non-missing observations (n), mean, SD, minimum, median and maximum for quantitative data. For categorical data, frequency counts and percentages will be determined. The denominator when calculating percentages will be the number of patients in the applicable analysis population. Descriptive statistics will be displayed for all visits that a measurement is collected on, even if the endpoint is only referring to limited visits for the analysis.

Baseline is defined as the last value measured prior to first study treatment administration, unless otherwise specified. In case this value is missing for a specific patient, but an earlier measurement (e.g. screening) is present, this value will be used as baseline instead. Unscheduled measurements are excluded as baseline value.

If available in the database, data for screening failures will not be presented in summary tables, except for disposition and end-of-study displays. Data for screening failures will be listed as available.

For patients that are unable to attend the clinic on a study visit due to ALS progression, at least ALSFRS score, AEs and concomitant medication data are collected. These data may be collected by telephone and are considered of the same quality as performed during live visits.

If a patient is not able to attend the site for two consecutive visits, then IMP will be discontinued at the 2nd missed visit, but participation in the trial and data collection can continue via telephonic visits to collect ALSFRS-R, AE and concomitant medication. It is assumed that data collected via telephone visits is of same quality as the data collected via site visits.

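### Repeating laboratory tests at Visit 1 only when screening was abnormal biases the within-arm change from baseline in creatine kinase, and possibly creatinine; the between-arm comparison is not affected

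*Protocol*

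**What the plan says.** **Which tests are repeated.** The notes to Table 1 of the protocol state: "Only labs parameters that are abnormal in the screening visit will be re-evaluated in baseline visit". Protocol 6.2 attaches the same restriction to the fasting routine bloods at Visit 1, and SAP 2.5 repeats it. Neither document defines abnormal.

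**Where CK and creatinine come from.** Protocol 6.2 says, in its baseline biomarker bullet: "Creatinine and creatine kinase will be measured in routine biochemistry lab testing". The Table 1 note on blood biomarkers also sends both to the biochemistry panel. No separate draw for them is described.

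**What counts as baseline.** SAP 5.1: "Baseline is defined as the last value measured prior to first study treatment administration, unless otherwise specified". If that value is missing, "but an earlier measurement (e.g. screening) is present, this value will be used as baseline instead". SAP 5.1 also says: "Unscheduled measurements are excluded as baseline value". Table 1 schedules chemistry at Visit 1, so a repeat done there is a scheduled value and this exclusion does not remove it.

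**What is reported.** Protocol 3.2.4 lists as an exploratory endpoint "Change from baseline in the ALS biomarkers creatinine and creatinine kinase". SAP 5.6.4 summarises it by treatment group. The output list in SAP 10.3 gives biomarkers descriptive tables and an out-of-range display, whereas SVC, the dynamometer score, ALSAQ-40 and VAS each also have a table of statistical results. SAP 5.7.2 shows CK and creatinine a second time among the safety laboratory data.

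**The concern.** Read together, these rules give two kinds of baseline. A patient whose screening value was normal keeps it. A patient whose value was abnormal has it replaced by a second draw a few days later. Screening values that are extreme partly by chance on the abnormal side are swapped for less extreme ones. Those that are extreme by chance on the normal side stay. The mean baseline is therefore pulled away from the abnormal side, while later values are not selected at all.

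The protocol's rationale for biomarkers indicates which side is abnormal. It says "Serum creatine kinase (CK) is increased in ALS patients" and "Plasma creatinine is a surrogate ALS biomarker of muscle mass and is decreased in ALS patients". For CK this makes baseline too low and produces an apparent later rise. For creatinine, if flags are mostly low, baseline is too high and an apparent later fall follows.

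At stake is how the by-arm biomarker summaries are read. The SAP plans no between-arm estimate for these two markers, so the number printed for each arm is the one that carries the bias.

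**Working it through.** The documents give no figure for this point, so there is none to reproduce.

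**Inputs from the documents.** Screening falls on Day -12 to Day -2 (protocol 6.1), so little true change is expected before Visit 1. The retest rule depends only on the screening result, so it acts identically in both arms. Planned numbers are 200 and 100.

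**Inputs that are assumptions.** These are the share flagged abnormal, the between- and within-patient standard deviations on the log scale, normality on that scale, and no true change.

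**Formula.** Let X1 be the screening value and X2 the Visit 1 repeat, each with mean μ and SD σ and with correlation ρ. Let the abnormal limit be high-side, at standardised position z. Baseline B is X1 if X1 is normal and X2 if it is not.

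- E[B] − μ = −σφ(z) + ρσφ(z) = −(1−ρ)σφ(z).
- Later values have mean μ, so the spurious change is +(1−ρ)σφ(z). For a low-side limit the sign reverses. With both limits the change is (1−ρ)σ[φ(z_high) − φ(z_low)].

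Only the correlation between screening and Visit 1 enters; how later values correlate with screening does not matter for the overall mean. The direction for CK does not need normality either. If X1 and X2 are exchangeable, pairs with both values above the limit cancel. The pairs left have X1 above and X2 at or below it, so the replaced values are on average higher than their replacements.

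**CK by formula** (φ = 0.399 at 50% flagged, 0.348 at 30%, 0.103 at 5%):

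- Middle case, ρ 0.8, σ 0.6, 50% high: 0.2 × 0.6 × 0.399 = 0.048, or +4.9%.
- ρ 0.9, σ 0.5, 30% high: 0.1 × 0.5 × 0.348 = 0.017, or +1.8%.
- ρ 0.6, σ 0.7, 50% high: 0.4 × 0.7 × 0.399 = 0.112, or +11.8%.
- Middle case with only 5% flagged: 0.2 × 0.6 × 0.103 = 0.012, or +1.2%.

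**CK by simulation** (2 million patients per row, no true change):

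| SD between / within | ρ | Share high | All patients | Normal value kept | Retested |
|---|---|---|---|---|---|
| 0.7 / 0.2 | 0.925 | 10% | +0.95% | +1.07% | −0.09% |
| 0.7 / 0.2 | 0.925 | 50% | +2.21% | +4.47% | +0.01% |
| 0.7 / 0.3 | 0.845 | 50% | +4.82% | +9.86% | 0.00% |
| 0.6 / 0.4 | 0.692 | 50% | +9.28% | +19.43% | −0.02% |

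The bias sits in patients whose normal value is kept. Those retested have an unselected baseline and show none.

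**Creatinine by simulation:**

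| SD between / within | Share low | Share high | All patients |
|---|---|---|---|
| 0.25 / 0.05 | 10% | 0 | −0.17% |
| 0.25 / 0.08 | 30% | 0 | −0.84% |
| 0.25 / 0.08 | 30% | 5% | −0.60% |
| 0.20 / 0.10 | 50% | 0 | −1.76% |
| 0.25 / 0.08 | 10% | 10% | 0.00% |
| 0.20 / 0.10 | 5% | 10% | +0.32% |

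**Within and between arms.** In 4,000 simulated trials of 200 and 100 patients with no true change, a nominal 5% test of within-arm CK change (SDs 0.7/0.3, 50% high) rejected 35% and 19% of the time. For creatinine (SDs 0.25/0.08, 30% low) it rejected 19% and 11%. The between-arm test rejected 5.8% and 4.3%, near its nominal level. The SAP plans neither test for these markers; the figures only show which contrast is safe.

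**After the change.** With the screening value as baseline for all, the overall spurious change is +0.01% (CK) and −0.01% (creatinine). With a Visit 1 value for all, it is −0.04% and +0.02%. All four are within simulation noise.

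**The case against.** The strongest objection is that this is a randomised, placebo-controlled trial and the summaries show both arms. Placebo carries the same offset, so anyone who compares the two columns is protected. That stands, and it limits the point. A reader might infer that the treatment effect on CK is biased, or that a real fall on FAB122 would be hidden. The documents do not support this, because the retest rule ignores arm.

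Second, the schedule marks a blood biomarker sample at baseline, and the matching note mentions creatinine and CK. If that means both are assayed in everyone at Visit 1, the problem disappears for these two markers. This stands as an open question. A reader might call protocol 6.2 contradictory, but its text sends both markers to the panel that the note restricts. It is ambiguous rather than in conflict.

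Third, abnormal might mean only values the investigator judges significant. Flag rates would then be low and the CK bias near the 1.2% shown above. This also stands.

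Fourth, the percentages are on the log scale, whereas SAP 5.1 plans arithmetic summaries and SAP 5.6.4 reserves geometric means for NFL. The direction for the CK mean carries over, but the percentages are not the statistic that will be printed.

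A reader might also infer that the artefact imitates disease progression. The protocol says CK is raised in ALS and associates it with progression. It does not say that CK rises within a patient as the disease advances.

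**Conclusion.** The point holds in a limited form. As written, the retest rule and the baseline definition together bias within-arm change from baseline in CK upward, by roughly 1–12% on the log scale. That range rests wholly on assumed flag rates, SDs and correlations. Creatinine shows a small spurious fall, about 1% or less in most scenarios and at most 1.8%, and only if low flags outnumber high ones. The protocol's description of creatinine in ALS and the exclusion of creatinine clearance below 50 mL/min make that plausible, but no flag rates are given. With equal flags the bias is nil, and with more high flags it reverses.

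All of this is conditional on CK and creatinine not being drawn from everyone at Visit 1. The FAB122–placebo difference is unbiased in expectation, both markers are exploratory, and no primary or key secondary endpoint is involved. The same mechanism reaches other laboratory parameters in the safety tables, but the documents give no basis for a size there. This is a minor improvement that is cheap to make.

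**What to change.** 1. In the protocol, state whether CK and creatinine are measured in every patient at Visit 1.
2. In SAP 5.6.4, state that for CK and creatinine the baseline is the screening value in every patient or, if Visit 1 values exist for everyone, the Visit 1 value in every patient. Selective Visit 1 repeats are listed only. Use the same baseline where SAP 5.7.2 shows these two again, so that the displays agree.
3. Report the between-arm difference beside the by-arm summaries of both markers.
4. Leave the last pre-dose baseline in place for the other safety laboratory tables, with a footnote that abnormal-only retesting affects within-arm change. Changing it there would discard valid Day 1 values, and screening baselines would still carry selection from the entry limits on ALT/AST and bilirubin.

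**Cost.** A short SAP addition, using data already collected. For retested patients the CK and creatinine baseline moves to 2–12 days before first dose, as it already is for the others. The creatinine clearance limit at entry may leave a slight residual selection in creatinine; CK has no entry limit.

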## **6.1. Screening and Eligibility Assessment**

Subjects will report to the clinical site for a screening examination between Day -12 and Day -2.

Prior to performing any study-related activities or evaluations, the patient must be thoroughly informed about all aspects of the study, including scheduled visits and activities. Patients will sign the study-specific consent form prior to any screening procedure. A signed copy of the informed consent form (ICF) should be provided to each consenting subject and with the original to be retained in the subject's study records. Depending on local regulations an independent ICF for Future Biomedical Research (FBR) should also be signed.

The following information and procedures will be performed and documented as part of the screening assessment:

- Assessment of eligibility according to inclusion/exclusion criteria
- Demographics, including sex, ethnic origin, date of birth
- Medical history including query for baseline signs/symptoms
- Review of prior and ongoing concomitant medications (taken in previous 30 days)
- Complete physical examination
- Neurological examination
- Height, weight and calculated BMI
- Vital signs measured with the subject in a supine/semi-supine position (for at least 5 minutes prior), including blood pressure, pulse rate, pulse oximetry and temperature

---

- Standard 12-lead ECG (subject should be in a supine/semi-supine position for at least 5 minutes prior to assessment)
- Nerve Conduction Study (NCS)
- Fasting blood samples for routine clinical labs (clinical chemistry, haematology). See table 2 for lab assessments.
- Blood samples for serology (HIV, and hepatitis B and C evaluations)
- Urine samples for urinalysis
- $\beta$ -hCG in plasma and urine pregnancy test only in women of childbearing potential
- ALS evaluation procedures: ALSFRS-R and Slow Vital Capacity (SVC)
- Plasma vitamin B6 levels, and, if necessary, vitamin B6 supplements (pyridoxine (100 mg/day)) will be prescribed

Compliance with inclusion criteria and exclusion criteria will be verified against information collected and documented in the database.

Once all inclusion criteria are met, exclusion criteria ruled out, and safety\* laboratory measurements obtained and reviewed, consenting subjects are eligible for randomization into the study.

\*Vit B6 is not considered a safety assessment at screening

## 6.2. Baseline Assessments

### Baseline (Visit 1) Week 0 (Day 1)

The following procedures will be performed:

- Assessment of eligibility according to inclusion/exclusion criteria
- Randomization

Eligible patients will be randomized strictly sequentially, according to a randomization list prepared by the Biostatistician

All patients will receive a unique patient identification number at screening visit when signing the informed consent and before any study procedures are performed. Three hundred patients will be randomized 2:1 in the following 2 groups:

1. 200 patients will receive FAB122 100mg/d + SOC

2. 100 patients will receive placebo + SOC

The investigators will randomize patients directly online. In case of discontinuation from the study, the randomization number will not be reused.

- Review of prior and ongoing concomitant medications
- Complete physical examination
- Neurological examination
- Weight
- Vital signs measured with the subject in a supine/semi-supine position (for at least 5 minutes prior), including blood pressure, pulse rate, pulse oximetry and temperature
- Standard 12-lead ECG (subject should be in a supine/semi-supine position for at least 5 minutes prior to assessment)
- Fasting blood samples for routine clinical labs (clinical chemistry, haematology). See table 2 for lab assessments.

**\* Only labs parameters that are abnormal in the screening visit will be re-evaluated in baseline visit.**

- Urine samples for urinalysis
- Urine pregnancy test only in women of childbearing potential
- Plasma vitamin B6 levels, and, if necessary, vitamin B6 supplements (pyridoxine (100 mg/day)) will be prescribed.
- ALS evaluation procedures: ALSFRS-R, Slow Vital Capacity (SVC), Hand-Held Dynamometry, ALSAQ-40, Edinburgh Cognitive and Behavioural ALS Screen (ECAS), EQ-5D-5L, VAS, King's staging system and MiToS.
- Blood sampling for biomarker: neurofilament light (NFL). Creatinine and creatine kinase will be measured in routine biochemistry lab testing.
- Urine collection for biomarkers: urinary extracellular domain of neurotrophin receptor p75 (Urinary P75ECD) and oxidative stress biomarker 8-hydroxyguanosine (8-OHdG)
- Blood sampling for genotyping for Future Biomedical Research (FBR) (if consented)

- Blood sampling for RNA and serum collection for FBR (if consented)
- Cerebrospinal fluid (CSF) sampling for Future Biomedical Research (if consented)
- Dispensing study Medication: Instructions for dosing FAB122 and first dosing
- Blood sampling for FAB122, in selected sites if consented. Specific ICF will be provided.
- Blood sampling for riluzole, in selected sites if consented. Specific ICF will be provided.
- Adverse Events monitoring
- Cost questionnaire

### 6.3. Subsequent Visits

#### Visit 2 Week 4 (Day 28 ±3Days)

The following procedures will be performed:

- Review ongoing concomitant medications
- Neurological examination
- Vital signs measured with the subject in a supine/semi-supine position (for at least 5 minutes prior), including blood pressure, pulse rate, pulse oximetry and temperature
- Fasting blood samples for routine clinical labs (clinical chemistry, haematology). See table 2 for lab assessments
- Urine samples for urinalysis
- Plasma vitamin B6 levels, and, if necessary, vitamin B6 supplements (pyridoxine (100 mg/day)) will be prescribed.
- ALS evaluation procedures: ALSFRS-R
- Blood sampling for biomarker: neurofilament light (NFL). Creatinine and creatine kinase will be measured in routine biochemistry lab testing.

- Urine collection for biomarkers: urinary extracellular domain of neurotrophin receptor p75 (Urinary P75ECD) and oxidative stress biomarker 8-hydroxyguanosine (8-OHdG)
- Blood sampling for FAB122, in selected sites if consented
- Blood sampling for riluzole, in selected sites if consented
- Nerve Conduction Study (NCS)
- Adverse Events monitoring
- Compliance check

**Visit 3 Week 12 (Day 84 ±3Days)**

The following procedures will be performed:

- Review ongoing concomitant medications
- Neurological examination
- Vital signs measured with the subject in a supine/semi-supine position (for at least 5 minutes prior), including blood pressure, pulse rate, pulse oximetry and temperature
- Fasting blood samples for routine clinical labs (clinical chemistry, haematology). See table 2 for lab assessments
- Urine samples for urinalysis
- Urine pregnancy test only in women of childbearing potential
- Plasma vitamin B6 levels, and, if necessary, vitamin B6 supplements (pyridoxine (100 mg/day)) will be prescribed
- ALS evaluation procedures: ALSFRS-R, Slow Vital Capacity (SVC), Hand-Held Dynamometry, King's staging system and MiToS, EQ-5D-5L and VAS
- Blood sampling for RNA and serum collection for FBR (if consented)
- Blood sampling for biomarker: neurofilament light (NFL). Creatinine and creatine kinase will be measured in routine biochemistry lab testing.

- Urine collection for biomarkers: urinary extracellular domain of neurotrophin receptor p75 (Urinary P75ECD) and oxidative stress biomarker 8-hydroxyguanosine (8-OHdG)
- Cerebrospinal fluid (CSF) sampling for Future Biomedical Research (if consented)
- Nerve Conduction Study (NCS)
- Adverse Events monitoring
- Cost questionnaire
- Dispensing study medication
- Compliance check

